STUDY PROTOCOL

TITLE OF THE STUDY

Diagnosis of Obstetric Anal Sphincter Injuries (OASIs) using Transperineal Ultrasound Scan (TPUS)

PROTOCOL VERSION NUMBER:

Version 2

RESEARCH REFERENCE NUMBER:

IRAS number 196995

DOCUMENT DATE:

21st December 2016

KEY STUDY CONTACTS

Research fellow	[name] ST5 in Obstetric and Gynaecology, University Hospital Lewisham [contact] E-mail: [contact]
Chief investigator	[name] Consultant Obstetrician and Gynaecologist, University Hospital Lewisham
Supervisors:	[name] Consultant Obstetrician and Gynaecologist, University Hospital Lewisham [name] Consultant Obstetrician and Urogynaecologist, Croydon University Hospital [name] [name] Consultant Obstetrician and Gynaecologist, Croydon University Hospital

	
[name]
 
Consultant Obstetrician and Gynaecologist,
 
Croydon University Hospital

--	---

STUDY SUMMARY

Study Title	Diagnosis of Obstetric Anal Sphincter Injuries (OASIs) using Transperineal Ultrasound Scan (TPUS)
Study Design	Prospective observational study
Study Participants	Women who undergoing their first vaginal delivery
Planned Size of Sample (if applicable)	216
Planned Study Period	January 2017 to April 2018
Research Question/Aim(s)	
1) HYPOTHESIS
 
- Transperineal Ultrasound Scan (TPUS) at delivery will increase the detection of Obstetric Anal Sphincter Injuries (OASIs).

2) PRIMARY AIM

- To determine whether the use of the transperineal ultrasound will improve the detection of OASIs immediately following vaginal delivery.

3) SECONDARY AIMS

- To measure hiatal dimensions during labour and correlate to levator detachments.
- To correlate intrapartum fetal head position and station identified using three-dimensional (3D) transperineal and transabdominal ultrasound with levator injury.
- To assess anal sphincter integrity immediately after primary repair of OASIs with transperineal ultrasound.

LIST of CONTENTS

GENERAL INFORMATION	
TITLE PAGE	1
KEY STUDY CONTACTS	2
STUDY SUMMARY	3,4
LIST of CONTENTS	5
STUDY FLOW CHART	6
SECTION	
1. BACKGROUND	7-12
2. RESEARCH QUESTION/AIM(S)	13
3. DESIGN AND METHODOLOGY	14-16
4. ETHICAL AND REGULATORY COMPLIANCE	17-18
5. REFERENCES	19- 23

STUDY PROTOCOL

BACKGROUND

Obstetric Anal Sphincter Injuries (OASIs)

The incidence of anal incontinence - “the involuntary loss of flatus, liquid or stool that is a social or hygienic problem” (1) is reported to occur in 20-68 % of women after Obstetric Anal Sphincter Injuries (OASIs) (2) (3) (4). Obstetric related anal incontinence was previously believed to be due to pudendal neuropathy (5) (6) (7). However with the advent of Endoanal Ultrasound Scan (EAUS) it has become apparent that mechanical trauma to the anal sphincter is the major aetiological factor.

Three dimensional (3D) EAUS is the gold standard tool to detect OASIs (8). It is however not available in most obstetric units. A potential alternative imaging modality is Transperineal Ultrasound Scan (TPUS) (9) (10) (11) (12) (13). TPUS is readily

available in all obstetric units and therefore potentially can be used as a diagnostic tool to detect OASIs. In addition, it allows assessment of the levator ani muscle (LAM), which is believed to play an important role in the maintenance of anal incontinence (14).

Comparative studies have been done between TPUS and EAUS and have shown a moderate to good correlation between the two imaging modalities for the evaluation of the anal sphincter complex (15) (16). Roos et al (17) compared TPUS with EAUS on women who had an OASIs or symptoms of anal incontinence without OASIs over 12 months following delivery. They found that TPUS is good at detecting normal anal sphincters. However, when an anal sphincter defect is detected with TPUS it requires further clinical assessment to determine whether an OASIs has actually occurred. The authors therefore recommended that if TPUS reveals an intact anal sphincter then no further test is necessary; however if TPUS reveals a defect, a clinical examination and EAUS should be performed to confirm damage to the anal sphincter. In a study by Oom et al (15), TPUS was able to detect 70% of cases with external anal sphincter (EAS) defects and all cases of internal anal sphincter (IAS) defects identified on EAUS. Roche et al (18) scanned 20 primiparous women found and found that two dimensional (2D) TPUS detected all defects identified using 2D EAUS. Ros et al (19) also demonstrated a good correlation with 3D EAUS when 3D TPUS is used to detect residual anal sphincter defects 3 months to 6 years after primary repair of OASIs.

It is known that OASIs can lead to anal incontinence especially when damage to the anal sphincter is not recognised at the time of delivery (20) (21). The incidence of clinically undetected OASIs has been shown to vary between 13 to 87% (11) (22) (23). Two clinical studies have demonstrated that when a trained doctor re-examined the perineum and anal sphincter that the rate of OASIs doubled (22) (24). This highlights the need to improve education of obstetricians and midwives in perineal anatomy and clinical diagnosis of OASIs. However despite training, doctors and midwives still fail to identify all OASIs (11) (25). Although EAUS can increase the detection rate of OASIs (22), it is not widely available in most UK obstetric units. In contrast, TPUS is available in most obstetric units and we therefore wish to determine whether TPUS in addition to a routine clinical examination will increase the detection rate of OASIs.

Anal incontinence can occur if OASIs are not repaired adequately (26) (27) (28). There is a significant correlation between the extent of an anal sphincter defect and the degree of anal incontinence (29). Ultrasound assessment between one week and one year after primary repair of OASIs has shown that between 16 to 90% (12) (28) (26) (15) (27) (30) have a residual anal sphincter defect. Women with a residual anal sphincter defect have significantly more symptoms of anal incontinence than those without a demonstrable defect (26). It is therefore not unreasonable to assume that some of these residual defects on scans represent injuries that were either not or incompletely repaired at the time of delivery. We therefore wish to investigate whether the use of TPUS immediately after primary repair of OASIs may be able to detect an inadequate repair which will be confirmed at the six to eight weeks follow-up.

The reported rates of anal incontinence following primary repair of OASIs range between 15 and 61% (31). Women with anal incontinence are more likely to have an EAS defect (26). We wish to perform a TPUS at six to eight weeks postpartum to assess the anal sphincter, and determine whether there are differences in the morphology compared to TPUS findings at delivery.

Hiatal dimension and levator ani avulsion

The incidence of levator ani muscle (LAM) avulsion is between 10 and 35% (32) (33) (34) (35) and can occur in up to 28% (33) of women undergoing their first vaginal delivery (32) (33). LAM avulsion can have a significant impact on faecal (13) (36) (37) (38) and urinary incontinence (39) (32) (40) (41) (42) (43) and sexual function (44) and is a major contributing factor to the development of pelvic organ prolapse (45) (46) (47) (34). Repairing LAM avulsion has been proven to be unsuccessful (48) (49). There have been attempts to try and find ways to prevent pelvic floor damage during vaginal delivery e.g EPI-NO ® (Tecsana GMBH, Muenchen, Germany). It is a mechanical device which is inserted into the vagina antenatally and stretches the vagina and perineum. However a recent randomized controlled trial has shown it to be of no benefit (50). Given that surgical repair and mechanical devices have been unsuccessful, research needs to focus on a better understanding of when these injuries occur in labour, with a view to preventing them happening in the first place.

A computerised model has demonstrated that the pelvic floor muscles undergo extensive stretching during a vaginal delivery (51). Several forms of injury have been described including avulsions, traumatic over-distension and hematomas (39) (52) (53). LAM avulsion have been investigated in labour and seem to only occur at delivery and not during the first and second stages of labour (54). However it is also known that smaller hiatal dimensions during the third trimester are found to be associated with a higher intervention rate for both instrumental deliveries and caesarean sections (55). Given that smaller hiatal dimensions in the third trimester lead to more obstetric intervention, it may be that particular dimensions or changes to these muscles in labour have an impact on the mode of delivery. Therefore performing TPUS in labour will give us a better understanding of the changes that occur in normal labour, and this may prove to be useful in prediction of mode of delivery.

Computerised models suggest that with the descent of the fetal head that there is distension of the pelvic floor muscles (51). The descent of the fetal head is usually determined by digital vaginal examination (DVE) in relation to the ischial spines and is called the fetal head station (56). This is however a subjective measure but can be measured objectively with TPUS (57) (58) (59) (58) (60). Therefore we wish to investigate changes to the pelvic floor muscles in relation to fetal head station objectively using TPUS.

Forceps delivery (61) (62) (63) (41) (64) (65) (45), prolonged second stage (66) (62) (67) and occipito-posterior (OP) position (33) are risk factors for LAM avulsion. The study evaluating OP with LAM avulsion were done as the baby was being delivered

when one can see the position of the baby's head (33). In labour the diagnosis of OP position was made by a DVE. However there is good evidence that diagnosing the position of the head by DVE can be difficult (68) and that ultrasound diagnosis is more accurate (69) (70) (71). Given that there have been no studies evaluating the position of the fetal head in labour and its relation to LAM avulsion, we propose to accurately diagnose fetal head position in labour and correlate it with LAM avulsion using TPUS.

In summary LAM avulsion and hiatal dimensions are associated with pelvic organ prolapse (45) (46) (47) (34) and both anal (13) (36) (37) (38) and urinary incontinence (39) (32) (40) (41) (42) (43). TPUS can be used to evaluate changes to these muscles in labour and also objectively measure fetal head station and position. This will be the first to study to evaluate these changes during normal labour. Understanding this is important so that preventative strategies can be developed to try and improve the quality of life for women.

HYPOTHESIS

- Transperineal ultrasound at delivery will increase the detection of OASIs.

AIMS OF THE STUDY

Primary Aim

- To determine whether the use of the transperineal ultrasound will improve the detection of OASIs immediately after vaginal delivery.

Secondary Aims

- To measure hiatal dimensions during labour and correlate to levator detachments.
- To correlate intrapartum fetal head position and station identified using three-dimensional (3D) transperineal and transabdominal ultrasound with levator injury.
- To assess anal sphincter integrity immediately after primary repair of OASIs with transperineal ultrasound.

DESIGN AND METHODOLOGY

Prospective study to be conducted between January 2017 and April 2018 at University Hospital Lewisham. Recruitment will start in January 2017 and stop in April 2018.

Sample identification

All women attending the hospital for routine anomaly ultrasound examinations between 20 and 22 weeks of gestation will be invited to participate and will be given an information leaflet at that stage. The initial approach will be made by a member of the clinical care team when women are admitted for induction of labour or are in labour on the delivery suite and the research team can then approach if the potential participant agrees to be approached. The research fellow (KW) will invite eligible women to participate in the study. The source of identifiable personal information that will be used to identify potential participants will be their maternity notes.

Patients inclusion criteria

The inclusion criteria are:

- women who are undergoing their first vaginal delivery
- 37 weeks of gestation or more
- a singleton pregnancy

- cephalic presentation
- maternal age 18 years old or more and being able to read and understand English.

Patients exclusion criteria

Exclusion criteria are those who do not fit in the inclusion criteria.

Size of sample

Power calculation: The incidence of clinically identified OASIS in nulliparous women is 6%. With increased surveillance with transperineal ultrasound and a detailed examination by a trained doctor we predict the detection rate of OASIS will be 12%. Assuming that 10% of the subjects will have discordant responses, and also assuming a 5% significance level and 80% power, it is calculated that 216 women would be required for the study.

Statistics

Due to the paired binary nature of the data (i.e. two measurements for each subject), the McNemar test will be used for the data analysis.

Method of evaluation

The research fellow (KW) will assess fetal head station and hiatal dimensions by TPUS and fetal head position by transabdominal ultrasound.

Perineal and anal sphincter trauma will be assessed and classified by the accoucher following vaginal delivery. Women will be re-examined by the research doctor (KW) who is trained in performing a detailed vaginal, perineal and rectal examination. When an OASIs is identified by the research fellow that is missed by the accoucher it will be verified by the consultant between 08.00 and 20.30 and by the ST6-7, specialty doctor or consultant out of hours and repaired.

Secondly TPUS will be performed to assess anal sphincter and hiatal dimension in the immediate postpartum period on all women in the study. TPUS will be repeated after the primary repair of OASIs to check the integrity of the anal sphincter. Images will be stored for independent assessment by experts in TPUS.

A follow-up appointment will be arranged for six to eight weeks later. At follow-up, all patients will be asked to complete a standardised questionnaire including symptoms of anal incontinence according to the St. Mark's Incontinence Score (SMIS) and undergo a repeat TPUS to assess the anal sphincter and hiatal dimensions.

Demographic and obstetric data will be collected prospectively from the maternity notes, including: maternal age, gestational age at delivery, parity, body mass index, history of previous caesarean section, spontaneous or induced labour, duration of first and second stage of labour, indication for operative vaginal delivery, final mode of delivery, mediolateral episiotomy, and neonatal weight. The following ultrasonographic data will also be collected: fetal head position, angle of progression, hiatal dimension, signs of levator avulsion, anal sphincter integrity.

ETHICAL CONSIDERATION

This study is a self-funded project. Information about the study will be given to women during the antenatal period. Those who agree to participate will be consented on admission to labour ward.

CONSENT

Informed consent will be obtained prior to participating. A discussion will be carried out between the potential participants and the research fellow (KW) about the nature and objectives of the study and possible risks associated with their participation. An

opportunity will be given to potential participants to ask questions. Written material (e.g. information leaflet and consent document) will be given.

REGULATORY COMPLIANCE

Before enrolling patients into the study, the chief investigator (KW) will apply for NHS permission from the NHS Research & Development (R&D). If there are any amendments that will potentially affect a site's NHS permission, the chief investigator will confirm with R&D department that NHS permission is on going.

[figure not shown]
PROTOCOL COMPLIANCE

Any accidental protocol deviations will be documented on the relevant forms and reported to the chief investigator.

DATA PROTECTION AND PATIENT CONFIDENTIALITY

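### Does giving recruitment and study conduct the same end month cut off the six-to-eight-week visit for the last women recruited?

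*Protocol*

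**What the plan says.** The Study Summary gives the planned study period as "January 2017 to April 2018". Design and Methodology opens with "Prospective study to be conducted between January 2017 and April 2018 at University Hospital Lewisham" and continues directly with "Recruitment will start in January 2017 and stop in April 2018". The study period, its conduct and recruitment therefore all end in the same month.

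Under Ethical Consideration, the protocol says of women who have had the antenatal information: "Those who agree to participate will be consented on admission to labour ward". Enrolment and delivery are thus close together in time.

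For what comes after delivery, Method of evaluation states "A follow-up appointment will be arranged for six to eight weeks later", and then "At follow-up, all patients will be asked to complete a standardised questionnaire including symptoms of anal incontinence", with a repeat transperineal scan (TPUS) of the anal sphincter and hiatal dimensions. The Background gives the same timing: "We wish to perform a TPUS at six to eight weeks postpartum to assess the anal sphincter". The text gives no later date for the last visit or the end of the study.

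**The concern.** If the study stops when recruitment stops, no time is left for a visit that comes six to eight weeks later. Women are enrolled in labour, so there is no gap between enrolment and delivery to absorb the difference. The conduct and recruitment dates stand in separate sentences, which suggests that they are meant as two different things, yet they carry the same months.

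If the end date were enforced literally, the last recruits would lose their incontinence score and repeat scan. This is the only planned visit after delivery. The Background relies on it to confirm any inadequate repair suspected on the scan after primary repair, and to compare sphincter morphology with the findings at delivery. Few obstetric anal sphincter injuries (OASIs) are expected, so losing even two or three would be noticeable in those descriptive comparisons.

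**Working it through.** **Inputs.** From the protocol: recruitment January 2017 to April 2018; visit at 6 to 8 weeks (42 to 56 days) after delivery; 216 women; 6% of OASIs identified clinically, 12% predicted with closer examination, 10% discordant, 5% significance, 80% power. Assumed, because the protocol gives months only and no accrual rate: calendar limits of 1 January 2017 and 30 April 2018, and uniform accrual of all 216 women over that time.

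**The plan's own figure.** For McNemar's test with discordant proportion 0.10 and difference d = 0.12 − 0.06 = 0.06, two-sided:

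n = [1.96 × √0.10 + 0.8416 × √(0.10 − 0.06²)]² / 0.06² = 215.7, which rounds up to 216.

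The stated sample size is reproduced. It contains no term for the later visit.

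**Visit windows for April 2018 deliveries.**

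| Delivery | 6 weeks | 8 weeks |
|---|---|---|
| 1 April 2018 | 13 May 2018 | 27 May 2018 |
| 30 April 2018 | 11 June 2018 | 25 June 2018 |

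Every woman delivering in April 2018 is due after the stated end, even if April is read as its last day.

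**Cut-off dates.** Counting back from 30 April 2018, 42 days gives 19 March and 56 days gives 5 March. Women delivering after 19 March have no part of their window inside the stated period. Those delivering from 6 to 19 March have a window that begins inside it and ends outside it.

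**How many women.** From 1 January 2017 to 30 April 2018 is 485 days inclusive.

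- Window wholly outside: 42/485 = 8.7%; 216 × 42/485 = 18.7, about 19 women.
- Window partly or wholly outside: 56/485 = 11.5%; 216 × 56/485 = 24.9, about 25 women.
- Difference: about 6 women, who could still be seen in April within the permitted window.

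The count that bears on the question is therefore 19. At the predicted 12%, about 26 OASIs are expected overall (216 × 0.12 = 25.9), of which about 2 (18.7 × 0.12 = 2.2) would be among these women.

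**Do the dates remove the visits?** Two readings are possible.

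- The April 2018 date is a hard stop on all activity. The visits of about 19 women are then lost, against the instruction that all patients are to be asked to complete the questionnaire and be scanned.
- The April 2018 date describes the planned enrolment period, and follow-up runs on from delivery. Every instruction about visits can then be carried out, and the last one falls by 25 June 2018.

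The first reading lets a planned calendar period override an explicit procedure for every woman. The text offers no support for it: it contains no closing date for follow-up, no data lock and no exemption for late recruits.

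**Which aims depend on the visit?** The primary aim concerns detection immediately after vaginal delivery, and the McNemar comparison belongs to it. The third secondary aim concerns sphincter integrity immediately after primary repair, assessed by the scan repeated at that time. The other two relate measurements in labour to levator injury; the protocol does not fix when that injury is read, and hiatal dimension is also scanned in the immediate postpartum period. The later visit serves the purposes described in the Background, but no listed aim names it.

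**The case for a change.** The strongest case for a change is that the document separates conduct from recruitment and then gives both the same end. Study dates belong in a protocol, so this is a conflict between stated items and not a gap left to the analysis plan. The 12% of women expected to have an OASI are the ones for whom the later visit matters most, and separate dates for the end of recruitment and the last visit would cost almost nothing.

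Most of this stands as a description. The dates do not fit together, and a careful editor would separate them. What does not stand is the step from there to lost data. The visit is fixed by its distance from delivery, not by a calendar date, and it is asked of everyone. A research team working to the visit schedule has no reason to turn away a woman due in May or June 2018. The target of 216 might also be reached before March 2018, in which case the overlap would never arise, although the protocol plans recruitment into April. The study flow chart is missing from the text available for this review, so it could not be checked for an end-of-follow-up date.

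**Conclusion.** No change to the plan follows. The inconsistency is genuine but clerical: the planned end date leaves out the six to eight weeks of follow-up that the same protocol requires. Assuming uniform accrual of 216 women to 30 April 2018, about 19 women (8.7%), with about 2 expected OASIs, have visit windows that fall wholly after the stated period. The date conflict itself does not depend on that assumption; only the counts do.

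Followed as written, the visit schedule brings these women back by late June 2018 with the same questionnaire and scan as everyone else. The primary comparison, the sample size and the assessments at delivery are the same under either reading of the dates. Rewording the dates would make the document neater but would change no estimate, test or conclusion.

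### The 216 women and 80% power are justified for TPUS plus a trained doctor's examination, whereas the hypothesis and primary aim are about TPUS, so the 80% is not shown to apply to TPUS

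*Protocol*

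**What the plan says.** The hypothesis in the Study Summary is that "Transperineal Ultrasound Scan (TPUS) at delivery will increase the detection of Obstetric Anal Sphincter Injuries (OASIs"). The primary aim under Aims of the Study is "To determine whether the use of the transperineal ultrasound will improve the detection of OASIs immediately after vaginal delivery". The Background gives the reason for the study in the same terms: "we therefore wish to determine whether TPUS in addition to a routine clinical examination will increase the detection rate of OASIs".

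The Size of sample section starts from 6% clinically identified OASIs in nulliparous women and continues: "With increased surveillance with transperineal ultrasound and a detailed examination by a trained doctor we predict the detection rate of OASIS will be 12" per cent. It adds "Assuming that 10% of the subjects will have discordant responses", a 5% significance level and 80% power, and arrives at 216 women. The Statistics section names the McNemar test for two measurements per woman but does not say which two.

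Method of evaluation describes three assessments: the accoucher's, a re-examination of the women by the trained research doctor, and then TPUS on all women. TPUS images are stored for independent expert assessment, and anal sphincter integrity is a separate ultrasound data item.

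**The concern.** The only effect size in the protocol belongs to two components used together. The hypothesis, aim and rationale name one of them. The other is unlikely to be minor on the protocol's own account: "Two clinical studies have demonstrated that when a trained doctor re-examined the perineum and anal sphincter that the rate of OASIs doubled".

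Either reading of the unnamed McNemar pair leaves a gap. If the pair is accoucher v combined assessment, the sample size fits but a significant result does not answer the aim, since trained re-examination could explain some or all of the gain. If the pair isolates TPUS, the result answers the aim, but the 12%, the 10% discordance and the 80% were stated for something else. At stake is a conclusion that credits ultrasound with a gain that came wholly or partly from a second, better-trained examiner.

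**Working it through.** **1. Reproduce 216.** Inputs from Size of sample: difference d = 0.12 − 0.06 = 0.06, discordant proportion ψ = 0.10, significance level 5% (taken as two-sided), power 80%. The usual paired-proportions formula is

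n = [z(0.975)·√ψ + z(0.80)·√(ψ − d²)]² / d²

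= [1.960 × √0.10 + 0.842 × √0.0964]² / 0.0036 = (0.6198 + 0.2613)² / 0.0036 = 215.65, rounded up to 216.

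The protocol's arithmetic is right. The two discordant cells solve b + c = 0.10 and b − c = 0.06, so b = 8% and c = 2%. At 216 women, enumeration gives power of 77% for the exact McNemar test and 84% for the uncorrected test. The stated 80% lies between them. All of this is for the combined assessment.

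**2. Look for the same inputs for TPUS.** The protocol gives no detection rate, gain or discordance for TPUS, either over the accoucher or over the trained examination. Every TPUS gain below is therefore an assumption.

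**3. Pairs in which TPUS can only add cases** (accoucher v accoucher plus TPUS; trained examination v trained examination plus TPUS). Here c = 0.

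- The exact two-sided test needs 6 added cases: 2 × 0.5⁶ = 0.031, whereas 2 × 0.5⁵ = 0.0625.
- The uncorrected statistic (b − c)²/(b + c) reduces to b, so 4 added cases are enough (4 > 3.84).
- Power is P(Bin(216, d) ≥ 6) for the exact test and P(Bin(216, d) ≥ 4) for the uncorrected test.

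| Assumed TPUS gain | Exact | Uncorrected |
|---|---|---|
| 2 points | 27% | 63% |
| 3 points | 63% | 89% |
| 4 points | 87% | 97% |

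Power of 80% is reached at a gain of about 3.6 points (exact) or 2.5 points (uncorrected).

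**4. Accoucher v TPUS alone.** Discordance can now run both ways. The Background makes this plausible. It reports one recommendation that "if TPUS reveals a defect, a clinical examination and EAUS should be performed to confirm damage to the anal sphincter", and another study in which "TPUS was able to detect 70% of cases with external anal sphincter (EAS) defects". Two versions are shown as exact/uncorrected power at 216, with the number needed from the formula in step 1.

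| Assumed TPUS gain | Discordance held at 10% | n for 80% | Opposite cell held at 2% | n for 80% |
|---|---|---|---|---|
| 5 points | 58/67% | 312 | 64/72% | 281 |
| 4 points | 38/48% | 489 | 47/57% | 391 |
| 3 points | 22/29% | 870 | 30/38% | 609 |

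Holding discordance at 10% while the gain shrinks makes the opposite cell grow: at 4 points it is (10% − 4%)/2 = 3%. The right-hand version keeps the 2% implied by the protocol and is the milder case.

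**The case against.** Several counter-arguments carry weight.

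- **No comparator is named.** The hypothesis and aim name TPUS but not what it is compared with, and the choice of McNemar pair could be made in an SAP that is not shown. It would therefore go too far to say that the protocol tests a contrast other than the one it hypothesises. This stands. What remains is that the sole justification of 216 and 80% is for a combined procedure that the hypothesis and aim do not name.
- **TPUS may be meant to work together with an examination.** The Background reports that a TPUS defect needs confirmation, so a combined assessment can be read as TPUS in practice. This holds only in part, because Method of evaluation has women re-examined regardless of what the scan shows.
- **The data allow a TPUS analysis.** TPUS is done on all women and sphincter integrity is recorded separately. This is true and makes the fix cheap. It does not supply the missing gain and discordance.

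A reader might also infer that the 12% was taken from the two re-examination studies, so that nothing is left for TPUS. The protocol does not say where the 12% comes from. That 6% to 12% is also a doubling does not establish the link.

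**Conclusion.** The mismatch is plain from the text. The planned size and power are justified for TPUS plus trained re-examination, while the hypothesis, aim and rationale concern TPUS. A significant result for accoucher v combined assessment could not be attributed to TPUS, and the 80% is not shown to be the power for TPUS.

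The conclusion stops there. A reader might go on to say that the study is underpowered for TPUS, but the documents do not support that. Under the assumptions above, power at 216 runs from 22% (3 points, two-way discordance held at 10%, exact test) to 97% (4 points, TPUS only adding cases, uncorrected test). So 216 may be too few or enough. The calculation of 216 itself is correct for its stated inputs. Confidence is high in the mismatch; no loss of power is claimed. It should be fixed, because the plan as written would let a combined gain be reported as a TPUS gain.

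**What to change.** Do one of two things.

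**Preferred: match the claim to the calculation.** Keep 6% v 12% and 216, name accoucher v combined assessment as the McNemar pair, and word the hypothesis, primary aim and conclusion as TPUS plus trained re-examination. This costs only text. The price is that the claim about TPUS alone is given up.

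**Alternative: match the calculation to the claim.** Name a primary McNemar pair that isolates TPUS. Accoucher v accoucher plus TPUS answers the Background's question. Trained examination v trained examination plus TPUS gives the yield beyond a trained examiner. Three conditions are needed:

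- The TPUS result should come from the stored images already intended for independent assessment, read without knowledge of the examination findings. The scan follows the re-examination, and no blinding is stated.
- A TPUS-only positive should count as a detected OASI only if confirmed under the study's existing verification. Otherwise false positives count as improved detection. The protocol should say how the timing of the image reading fits with that verification.
- The pair's assumed difference, discordance and power at 216 should be restated, and the gain from trained re-examination reported separately.

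This needs no extra visits or scans, but it does need rules for the reading and for confirmation. The power stated for TPUS may fall below 80%.

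### Does the target of 216 leave open whether women who have a caesarean after consenting in labour are counted?

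*Protocol*

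**What the plan says.** All references are to the Protocol.

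- **Timing.** Under Sample identification, the clinical team makes the first approach "when women are admitted for induction of labour or are in labour on the delivery suite". Under Ethical Consideration, "Those who agree to participate will be consented on admission to labour ward". The Consent section adds: "Informed consent will be obtained prior to participating". The secondary aims include measuring hiatal dimensions during labour, so study scanning can begin before birth.
- **Eligibility.** The first inclusion criterion is "women who are undergoing their first vaginal delivery". The whole exclusion rule is: "Exclusion criteria are those who do not fit in the inclusion criteria".
- **Sample size.** Size of sample takes detection rates of 6% and 12%, 10% discordant responses, a 5% significance level and 80% power, and ends: "it is calculated that 216 women would be required for the study". The Study Summary gives 216 as the planned size. The row that describes participants, just before it, names women having their first vaginal delivery.
- **Measurement.** Statistics chooses the McNemar test because there are "two measurements for each subject". Under Method of evaluation, the accoucher classifies trauma after vaginal delivery, the research doctor re-examines, and transperineal ultrasound is done "in the immediate postpartum period on all women in the study".

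**The concern.** A woman can consent on admission, be scanned in labour and then have a caesarean. By the consent text she has entered the study. By the inclusion criterion, read as a vaginal delivery that actually happens, she does not belong in it. If the criterion is read as an intended vaginal delivery, she stays in but cannot supply the accoucher's assessment that forms half of the McNemar pair. The Background adds a reason to wonder about such women, since it hopes that ultrasound in labour may help to predict mode of delivery. No sentence in the visible text says whether she is withdrawn, replaced or counted.

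This would matter because 216 carries no margin. If it were a ceiling on consents with no replacement, every caesarean would cost a pair and power would fall below the stated 80%.

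**Working it through.** **1. Reproduce 216.** Inputs from Size of sample: paired difference d = 0.12 − 0.06 = 0.06; discordant share p = 0.10, which splits as (0.10 + 0.06)/2 = 0.08 in one direction and 0.02 in the other; significance level 5%; power 80%. The section does not state sidedness. The two-sided version gives the stated figure (a one-sided test would give 170).

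n = [1.96·√p + 0.8416·√(p − d²)]² / d²

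= [1.96·√0.10 + 0.8416·√0.0964]² / 0.0036 = 215.65, rounded up to 216.

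**2. Power at 216 pairs.**

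Power = Φ{(d·√n − 1.96·√p) / √(p − d²)}

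= Φ{(0.06·√216 − 1.96·√0.10) / √0.0964} = 80.1%.

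So 216 is the number of complete pairs, without inflation. The arithmetic is right, and the only question is which women it counts.

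**3. Set the text side by side.**

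| Place | What it implies for the 216 |
|---|---|
| Study Summary | The population is women having a first vaginal delivery; the planned size follows in the next row |
| Primary aim | Detection is studied immediately after vaginal delivery |
| Inclusion and exclusion criteria | Women who do not fit the vaginal-delivery criterion are out |
| Size of sample, Statistics | Discordance is a property of subjects, each with two measurements |
| Method of evaluation | The accoucher's assessment exists only after vaginal delivery |
| Data collected | An indication is recorded for operative vaginal delivery; none is listed for caesarean |

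Every row fits 216 as vaginally delivered women with both assessments. The consent text fits it too: asking for consent first, and keeping those who meet a criterion settled at birth, is a sequence and not a contradiction.

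**4. What the other reading needs.** It needs 216 to be a limit on consents, without replacement. No section says so. Recruitment is set by dates, January 2017 to April 2018. The Protocol gives no rate of caesarean after consent, so any loss is an assumption. Using the formula in step 2, a loss of 5% would leave 205 pairs and 78.0% power; 10%, 194 pairs and 75.7%; 20%, 173 pairs and 70.7%; 30%, 151 pairs and 64.7%. These figures describe a scenario that the Protocol does not set out. They do not measure an error in it.

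**The case for a change.** The strongest case for a change is that eligibility and the enrolment target belong in the protocol and have to be applied on the labour ward, before any analysis plan comes into play. Women consented on admission are a wider group than women who deliver vaginally, and no sentence ties 216 explicitly to the narrower group. Recruitment has a calendar end, and nothing states that it continues until 216 pairs exist. Reading the criterion as intended delivery sharpens the question, because the woman then remains a participant without a pair.

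Part of this stands. The visible text has no explicit rule for caesarean after consent, and the criterion's wording can be read as intention. But the two readings of the criterion lead to the same analysed group: on one she is excluded, and on the other she yields no pair and cannot enter a McNemar table. The count that the calculation refers to is therefore the same. The study flow chart is also not shown in the copy at hand and may set out the path from consent to analysis, so silence in the text is weak evidence of a gap in the plan.

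**Conclusion.** The concern does not call for a change. The number 216 is correct for its stated inputs (215.65, rounded up), it counts complete pairs, and the Study Summary, the eligibility rules and the paired analysis together identify those pairs as women with a first vaginal delivery and both assessments. On that basis the power is 80.1% and the McNemar test is unaffected. No stated rule produces a wrong result, and no loss of power is demonstrated.

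What is left is a missing definition that those running the study would fill sensibly: a woman delivered by caesarean after consent gives no pair and does not count towards the target. Writing this down would be harmless but would alter neither the sample size nor the analysis. The conclusion assumes a two-sided test, which the Protocol does not state but which reproduces its figure, and it assumes that the flow chart, which could not be seen, does not define 216 as women consented.
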